Date: February 20, 2017
Version Number: 11
Principal Investigator: [name]
Application Number: 1212915
Application Title:

Does Optimized General Anesthesia Care Reduce Postoperative Delirium In Older Patients Undergoing Hip Fracture Repair?

Protocol

1. Abstract

The overall objective of this proposal is to determine if optimized general anesthesia care of elderly patients undergoing hip fracture surgery will minimize postoperative delirium (POD) and improve postoperative outcomes. A proactive geriatric consultation using a multifactorial bundle of pharmacological and non-pharmacological strategies in the perioperative period has been shown to effectively reduce POD, but even with these perioperative medical interventions, more than 30% of patients undergoing hip fracture surgery experience POD.^{1,2}

There is tantalizing preliminary evidence suggesting that intraoperative interventions may also have the potential to further decrease POD.³⁻⁶ This prospective randomized clinical trial (RCT) will focus on the intraoperative optimization of: 1. blood pressure, 2. depth of anesthesia, 3. cerebral oxygenation, and 4. postoperative pain management in an effort to further reduce POD. All of these interventions can easily be managed by anesthesia providers during surgery. A total of 160 patients will be randomized to optimal versus usual anesthesia care for hip fracture surgery to determine the impact of this targeted anesthesia care bundle on the severity and incidence of POD. The results of our proposed study are intended to enhance patient safety by developing a relatively easily implemented, generalizable anesthesia management strategy that can be used by anesthesia providers in both academic and private settings. This proposal has the potential to further reduce POD, thereby decreasing patient morbidity and mortality.

2. Objectives (include all primary and secondary objectives)

The primary objective of this proposal is to develop an optimized general anesthetic plan, focusing on anesthetic depth, blood pressure control, and cerebral oxygenation for elders undergoing hip fracture surgery. This protocol will compare usual care to optimal general anesthesia care to test the following hypotheses:

The use of an optimized general anesthetic technique for elders undergoing hip fracture surgery will:

- **Primary hypothesis: decrease the severity of POD**
- **Secondary hypothesis 1: decrease the incidence and duration of POD**

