- **Secondary hypothesis 2: decrease the length of stay in the hospital**
- **Secondary hypothesis 3: to determine if poor performance on preoperative cognitive tests or preoperative depression identify patients at high-risk for POD**
- **Secondary hypothesis 4: to determine if the level of preoperative inflammation predicts patients at risk for POD**

3. Background

Postoperative delirium (POD) is common in elderly patients and is reported to occur in 35 to 65% of patients undergoing hip fracture surgery.⁸ Despite the fact that delirium is a temporary condition, it is a medical and societal stressor from an economic and healthcare standpoint. POD is independently associated with increased morbidity, mortality, length of hospital stay, and placement in long-term care institutions. It increases the cost of hospitalization by \$4000 for each patient who develops this complication and the total costs attributed to the treatment of delirium in the US are estimated to be as high as \$152 billion each year.^{9,10}

The etiology of POD is multifactorial and involves a complex interaction between a vulnerable patient with preoperative risk factors who is exposed to numerous ***precipitating factors in the perioperative period.***¹¹ Most of the preoperative risk factors such as age, comorbidities and cognitive status are fixed and cannot be modified during the perioperative period. However, there are perioperative factors that are directly under the control of the anesthesia provider that could potentially be modified to minimize POD.

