To assess the **primary hypothesis**, the DRS-R98, a 16-item clinician-rated scale with 13 severity items and 3 diagnostic items (maximum total score of 46 and a maximum severity score of 39 points) will be utilized.³¹ The DRS-R98 is widely utilized in clinical and research situations when a sensitive, valid standardized measurement of delirium is needed. For the **secondary hypotheses**, we will collect data on the incidence of POD which will be a dichotomous outcome. The duration of delirium episodes and length of stay in the hospital will be measured in days and analyzed as a continuous variable.

Statistical Analysis: Group comparisons on the delirium severity score and length of stay will be made using the Wilcoxon Rank Sum Test (WRST). The WRST is a nonparametric alternative to the two sample t-test. The standard assumptions of the t-test are normality and equal variances, neither of which is required for the WRST. Hospital length of stay (LOS) is typically a highly skewed outcome due to a relatively few patients having atypically long LOS. Thus the WRST will also be used for a simple two-group comparison and results reported in terms of median LOS. Log-transformed LOS will be the dependent variable if regression analysis is needed for covariate adjustment.

Randomization only *guarantees* homogeneous groups when randomizing a very large number of subjects. Thus, preliminary comparison of the baseline characteristics of the usual care and study group will be performed to confirm that randomization did indeed produce similar groups with respect to demographics and initial cognitive status. Any statistically significant ($p < 0.05$) differences that are also judged to be clinically meaningful will shift the analytical approach to an analysis of covariance using either parametric or non-parametric regression methods most appropriate to the specific outcome.

We will also collect data on intraoperative variables including the average BIS and BP as well as the proportion of time that the BP and BIS is in the recommended range. This information will be analyzed as a quality control measure to ensure compliance with the treatment protocol in the optimal care group.

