Data for the treatment group (OP Care) will be analyzed after the first 5 patients and then after each additional 15 patients are treated to ensure compliance with the treatment protocol (BP and BIS in recommended range). Patients will be followed daily during the hospitalization and charts reviewed to determine transfusion requirements and prevalence and types of postoperative complications.

Power Analysis: The primary hypothesis states that optimized anesthesia care will decrease the severity of POD compared to usual care. We expect that the severity score in the optimized group will be 14 ± 3 versus 18 ± 4 in the usual care group similar to that seen in previous treatment studies.³⁵ To have 80% power to detect such a difference when testing a two sided alternative and alpha of 0.05 will require 22 subjects per group. This is the number of subjects that qualify as confused. Only patients with POD contribute to the DRS severity sample, so if 30% of subjects are expected to experience delirium, then the total sample size for the study would have to be $44/.3 = 148$, or 74 per group. We plan to enroll 80 patients per group for a total sample size of 160.

Interim Analysis: There will be no interim analyses and no safety monitoring board so there are no early stopping rules.

Data management

The data collected on the data collection forms developed for this study, will be obtained specifically for research purposes. Research data will be stored in a locked research office in the Department of Anesthesiology at the University Hospital. All patient identifiable information will be stored in a locked file cabinet in this locked research office or stored on a secure server in this locked office. Only research personnel listed on the IRB proposal will know the log in and password information for this server. The demographic, hemodynamic, laboratory and historical data that are collected at the time of the intraoperative study are part of the routine medical record documenting the patient's care in the perioperative period. The patient's identity will be specifically protected and confidentiality will be maintained in any publication of data.

8. Risks

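### Length of stay is ranked in plain days with no provision for in-hospital death, so early deaths count as short stays and an imbalance in them tilts the comparison

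*Combined protocol and SAP*

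**What the plan says.** Section 2 (Objectives) states Secondary hypothesis 2: optimized care will "decrease the length of stay in the hospital". A lower value is therefore the favourable direction.

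Section 7 (Study Statistics, Outcome Variables) fixes the scale: "The duration of delirium episodes and length of stay in the hospital will be measured in days and analyzed as a continuous variable". Under Statistical Analysis, LOS is compared between groups by the Wilcoxon rank sum test, with "results reported in terms of median LOS". For the adjusted case: "Log-transformed LOS will be the dependent variable if regression analysis is needed for covariate adjustment".

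Neither part of Section 7 excludes, censors or re-ranks a patient who dies before discharge. Section 7 plans a chart review for transfusion and postoperative complications, and Section 4 plans contacts at 3 months and 1 year for complications, function and living environment. Neither names death. Mortality appears in the Abstract as a hoped-for benefit ("thereby decreasing patient morbidity and mortality") and in the Background, but it is not listed as an outcome.

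**The concern.** Days in hospital end either at live discharge or at death, and the written rule does not tell them apart. A patient who dies on day 2 has a 2-day stay, which ranks among the best results in the trial on an endpoint where shorter is better.

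Some deaths are foreseeable in patients aged 65 or older with hip fracture, and the Background links delirium to mortality. If optimized care prevented early deaths, this endpoint would count against it. If it caused them, the endpoint would count in its favour. With no planned tabulation of in-hospital deaths by arm, a shorter median stay could be reported without the figure needed to interpret it.

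**Working it through.** The plan gives no effect size, variance or power for LOS, so there is no LOS figure of its own to reproduce. The check is of direction and size.

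**Inputs from the documents.** 80 patients per arm ("We plan to enroll 80 patients per group for a total sample size of 160"), Wilcoxon test, shorter is better. The two-sided 0.05 level is stated for the primary endpoint and is assumed here for LOS.

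**Assumed inputs.** LOS is log-normal with median 5 days and log SD 0.45, rounded up to whole days, and is the same in survivors of both arms. Death days are spread evenly over the ranges shown below. Illustrative death rates are 2% to 6% per arm.

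**Direction.** Let d_OP and d_UC be the proportions dying before any discharge. With identical survivors, the probability that an optimized-care patient has the shorter stay (ties counted half) is:

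- plain days: 0.5 + (d_OP − d_UC)/2
- deaths given the worst rank: 0.5 − (d_OP − d_UC)/2

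At 6% against 2%, plain days give 0.5 + 0.04/2 = 0.52, which favours the arm with more deaths. Worst rank gives 0.48. A simulation with log SD 0.5 and deaths on days 1 to 3 gave 0.518 and 0.480. At 4% against 4% the plain-day value was 0.501.

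**Largest possible size.** The SD of the rank sum is sqrt(80 × 80 × 161/12) = 293.

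- Moving one patient from the middle of the ranking to the best end changes the statistic by 40, or 40/293 = 0.137 in z. Four excess deaths give at most 4 × 0.137 = 0.55.
- Moving one patient from the best end to the worst end changes it by 80, or 80/293 = 0.273. Four give at most 1.09.

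The first quantity is the distortion that plain-day scoring adds. The second is the gap between two scoring rules, and half of it is the worst-rank penalty itself.

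**Size under the assumptions.** Mean shift in z towards the arm with more deaths under plain-day scoring, relative to leaving the deaths out:

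| Days on which deaths fall | Four excess deaths | Net excess of two |
|---|---|---|
| 1–3 | 0.52 | 0.26 |
| 1–5 | 0.40 | 0.20 |
| 1–7 | 0.23 | 0.12 |
| 1–10 | 0.04 | 0.02 |
| 3–12 | −0.17 | −0.08 |

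With three deaths in each arm the mean shift was zero in every row. Leaving deaths out is used only as a neutral reference here, not as a recommended analysis.

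**Effect on p.** Suppose the arm with fewer deaths would otherwise show z = 1.96 in its favour (p = 0.05). A shift of 0.4 leaves 1.96 − 0.4 = 1.56, or p of about 0.12. A shift of 0.2 leaves 1.76, or p of about 0.08.

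**The case against.** The strongest reply is that the plan never says deaths count as short stays. It is silent, and an analyst might leave deaths out. That is correct, and a reader should not infer that the plan contains an explicit rule scoring death as a good outcome. The silence still matters. The written method, followed without addition, has that effect, while dropping deaths would be an unwritten choice that compares survivors only.

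A second reply concerns size. A reader might take the 0.9 to 1.1 change in z for four deaths, which would move p=0.05 to between 0.28 and 0.38, as the bias. It is not: it is the gap between plain-day and worst-rank scoring, which answer different questions. The distortion from plain days is roughly half of that or less.

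Third, the effect needs deaths to be both early and unbalanced, and the documents show neither. If true mortality were equal at 2% to 4% per arm, an excess of four or more deaths in a given arm would arise by chance in only about 2% to 8% of trials. This stands and limits the weight of the point.

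Fourth, raw bed-days are a legitimate measure of resource use, and the Background does discuss hospital cost. This also stands. It is a reason to keep bed-days as a descriptive summary, but Secondary hypothesis 2 is set among hypotheses about patient benefit, where a stay ended by death should not count as a gain.

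**Conclusion.** The point holds as a gap in the LOS analysis with a predictable direction. Applied as written, the method ranks a death before typical discharge as a favourable stay, and the comparison moves towards whichever arm has more such deaths.

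The likely size is modest: about 0.4 in z for four excess deaths on days 1 to 5, about 0.2 for a net excess of two, and near zero with equal deaths or with deaths spread over days 1 to 10. The sign reverses if deaths are late. These figures rest on an assumed death rate, death timing and LOS distribution, none of which the documents supply, so the size cannot be settled from them.

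LOS is a secondary endpoint. The primary analysis of delirium severity and the total of 160 are unaffected.

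**What to change.** In Section 7, Statistical Analysis, state that patients who die in hospital take the worst rank (longer than any observed stay) in the Wilcoxon comparison, so that the endpoint is time to discharge alive. Report the number of in-hospital deaths by arm beside median LOS. Raw bed-days can stay as a descriptive measure of resource use.

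If the covariate-adjusted analysis is triggered, log LOS regression has the same gap. A model for time to live discharge with death as a competing event is one option. It is a larger change on which statisticians may differ, so it need not be a condition of the main fix.

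The main fix costs a sentence or two of text. It should need no new data, since patients are already followed daily in hospital and their charts reviewed. The downside is that the tested outcome becomes a combination of death and stay rather than bed-days alone, and the report should say so.

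### A baseline significance test plus an undefined judgement decides whether severity and length of stay are adjusted; fixing a rank-based adjustment for MMSE-2 and age in advance is a cheap improvement

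*Combined protocol and SAP*

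**What the plan says.** All of this is in the combined protocol and SAP, section 7 (Study Statistics).

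- **Default.** "Group comparisons on the delirium severity score and length of stay will be made using the Wilcoxon Rank Sum Test (WRST"). For LOS the Wilcoxon test is justified by skewness from a few unusually long stays, with "results reported in terms of median LOS".
- **Baseline check.** A preliminary comparison is to confirm that randomisation gave "similar groups with respect to demographics and initial cognitive status". The individual variables are not listed.
- **Switch.** For baseline variables on which the arms differ at p < 0.05, the plan states: "differences that are also judged to be clinically meaningful will shift the analytical approach to an analysis of covariance". The form of the adjusted analysis is left open; the text allows for "using either parametric or non-parametric regression methods most appropriate to the specific outcome".
- **Adjusted LOS model.** "Log-transformed LOS will be the dependent variable if regression analysis is needed for covariate adjustment". No adjusted model is named for severity, and no covariates are named for either outcome.
- **Severity sample.** The power analysis states: "Only patients with POD contribute to the DRS severity sample".

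The text does not say who judges clinical meaningfulness, by what threshold, or whether that person has seen outcomes by arm.

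**The concern.** Under proper randomisation every baseline difference arises by chance, and its p-value says nothing about how strongly the variable predicts the outcome. A strongly prognostic variable at p = 0.06 is left out, while an irrelevant one at p = 0.04 can bring in a covariate. The check also appears to be made in all 160 randomised patients, whereas severity is analysed only in those who develop postoperative delirium (POD), about 44 in the plan's calculation. Balance in the first set need not describe the second.

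Once the rule fires, two analysts who both follow the text could report different primary p-values, because the judgement and the severity model are open. Three things are at stake: avoidable discretion over the primary analysis, some conditional bias when a prognostic imbalance narrowly misses the threshold, and precision given up if the covariates matter.

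**Working it through.** **Inputs from the documents.** 80 patients per arm; 22 POD cases per arm; severity 14 ± 3 versus 18 ± 4; two-sided alpha 0.05.

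**Assumptions.** The covariate-outcome correlation r, the number of baseline variables tested, and the shape of the LOS distribution. The documents give none of these.

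**The plan's own figure.** With pooled variance (9 + 16)/2 = 12.5, n per arm = 2 × 12.5 × (1.96 + 0.84)² / 4² ≈ 12.3, so 13 (14 with the t distribution). The stated 22 is therefore not reproduced at 80% power. At 22 per arm, t-test power is 95.6%. That is a separate matter, but it explains why the severity powers below start near 94% and leave little room for gain.

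**How often the rule can fire.** For k independent variables, P(at least one p < 0.05) = 1 - 0.95^k. This is 9.8% for k = 2, 22.6% for k = 5 and 33.7% for k = 8. Five variables with the three cognitive tests correlated at an assumed 0.5 give about 21%. These are upper limits on how often the analysis shifts, because the judgement of meaningfulness must also be met.

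**Severity power.** Simulation of 60,000 trials per cell: two baseline covariates, one prognostic, tested in all 160; integer scores in 22 POD cases per arm. The rule uses Wilcoxon unless triggered, then rank regression on the triggered covariates. The alternative is rank regression on both covariates in every trial.

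| r | Rule, % | Always adjusted, % | Difference, points |
|---|---|---|---|
| 0 | 94.34 | 93.59 | -0.8 |
| 0.1 | 94.23 | 93.60 | -0.6 |
| 0.2 | 94.33 | 94.21 | -0.1 |
| 0.3 | 94.36 | 95.09 | +0.7 |
| 0.4 | 94.44 | 96.26 | +1.8 |
| 0.5 | 94.61 | 97.59 | +3.0 |

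A separate run of 4,000 trials per cell agreed: 94.1 versus 93.2 at r = 0, 94.2 versus 95.3 at r = 0.3, and 95.2 versus 97.9 at r = 0.5. The results hardly change if the odds of POD double per SD of the covariate.

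**Type I error, severity.** Overall, the rule gives 4.69% to 4.98% and always adjusting gives 4.93% to 5.12%. As an upper bound on discretion, suppose the analyst takes the smallest p of Wilcoxon, rank regression and linear regression whenever the rule fires. This gives 5.3% overall and 6.5% to 7.8% within the triggered trials.

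**Near-miss imbalance.** A baseline p between 0.05 and 0.20 occurs in 0.20 - 0.05 = 15% of trials per covariate. In those trials the rule's type I error for severity is 5.1% to 5.2% at r = 0.3 and 6.0% to 6.2% at r = 0.5. For LOS, assumed log-normal, it is 4.9% at r = 0, 6.2% at r = 0.3 and 8.6% at r = 0.5; always adjusting gives 4.9% to 5.2%.

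**LOS power, assuming 8% very long stays.** One simulation gave:

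| r | Wilcoxon, % | Adjusted log-LOS, % | Adjusted rank regression, % |
|---|---|---|---|
| 0 | 63.4 | 47.8 | 63.3 |
| 0.5 | 64.5 | 53.0 | 71.9 |

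Log-LOS regression thus loses 63.4 - 47.8 = 15.6 points and 64.5 - 53.0 = 11.5 points to Wilcoxon. A second simulation, also assuming 8% very long stays, gave losses of 11.4 points at r = 0 (64.4 versus 53.0), 7.5 at r = 0.3 (65.3 versus 57.8) and none at r = 0.5. With purely log-normal stays, log-LOS regression instead gains about 1, 5 and 11 points at r = 0, 0.3 and 0.5.

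**The case against.** The strongest case for leaving the plan alone is that it does little measurable harm to the primary endpoint. Overall type I error is controlled, even worst-case selection among models reaches only 5.3%, and always adjusting loses a little power when r is about 0.2 or less. This stands, and it sets the weight of the point.

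The rule is also not wholly open. It uses baseline data only, limits the check to two domains, names the log-LOS model, and calls the check preliminary, which suggests that it precedes the outcome analysis. The delirium specialist is blinded to assignment and baseline cognitive scores. These safeguards are real. But blinded assessment does not govern a later choice of model, and nothing says that the person judging meaningfulness has not seen outcomes by arm.

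A reader might infer from sections 3 and 8, which name age and cognitive status as risk factors, that adjusting for them must sharpen the severity comparison. The documents do not support that. They link these factors to the occurrence of POD, whereas severity is compared only among patients who already have it.

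A reader might also infer that the log-LOS model, being already named, should simply be used in every trial. The plan makes it conditional, and its own expectation of a few atypically long stays describes the setting in which that model can do worse than Wilcoxon. This objection stands and shapes the fix.

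**Conclusion.** The point holds as a cheap improvement. The trigger measures the wrong quantity and leaves the judgement and the severity model open in up to about 10% to 34% of trials, for an assumed 2 to 8 independent variables. A reader might infer that the two-stage rule inflates the false-positive rate. Followed mechanically it does not; the excess appears only in subsets (near-miss imbalance in a prognostic covariate) or if the analyst picks among models.

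For severity, the effect of always adjusting runs from a loss of about 0.8 points to a gain of about 3, depending on an r that the documents do not give. The case for change therefore rests mainly on fixing the analysis in advance. For LOS, the conclusion that log-LOS regression should not be the main analysis rests on the assumed tail: the loss is roughly 10 to 15 points with 8% very long stays and weak covariates, and log-normal data would reverse it. In the simulation that included it, rank regression matched Wilcoxon at r = 0 and beat it at r = 0.5.

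The point is confined to severity and LOS. No incidence model was examined, and adjustment does not repair the restriction of the severity sample to patients who become delirious after randomisation.

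**What to change.** Amend the statistical analysis text in section 7 before outcomes are examined unblinded:

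1. Delete the significance trigger and the meaningfulness judgement. Keep the baseline table as description.
2. Prespecify adjustment for baseline MMSE-2 and age regardless of observed balance.
3. For severity in POD cases and for LOS, regress the outcome ranks (mid-ranks for ties) on treatment, ranked MMSE-2 and ranked age, with a two-sided test of the treatment coefficient.
4. Report medians by arm for both outcomes, because a coefficient on the rank scale is not in points or days.
5. Report the unadjusted Wilcoxon test as a sensitivity analysis. Do not make log-LOS regression the main LOS analysis.
6. State how an incomplete MMSE-2 is handled, for example by imputation from baseline data without regard to arm. The score gates randomisation, but section 8 lets patients stop testing.

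**Cost.** A short amendment, with no new data, visits or patients. It uses two degrees of freedom: about 0.8 power points for severity at the planned effect if neither covariate is prognostic, and up to about 1.4 points if the true effect is small enough to give only 80% power. With 10% of MMSE-2 scores missing and mean-imputed blind to arm, severity type I error stays at 4.9% to 5.1%, and the gain at r = 0.5 falls from 3.0 to 2.5 points.
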